This Statistical Analysis Plan (SAP) for trial NN7999-4670 is based on the protocol *A multi-centre, open-label trial evaluating efficacy, safety and pharmacokinetics of nonacog beta pegol when used for treatment and prophylaxis of bleeding episodes in Chinese patients with haemophilia B*, version 1.0 dated 21Jan2021.

Table 1 SAP Version History Summary

SAP Version	Approval Date	Change	Rationale
1		Not Applicable	Original version

1 Introduction

The rationale for this phase 3b trial is to investigate the efficacy, safety and pharmacokinetics of nonacog beta pegol used for treatment of bleeding episodes and for prophylaxis in Chinese patients with moderate to severe haemophilia B (FIX activity $\leq 2\%$) in order to enable a comparison of efficacy, safety and pharmacokinetic data from the current trial in Chinese patients with data from the global pivotal phase 3a trial with nonacog beta pegol (Trial NN7999-3747).

Specifications of tables, figures and listings (TFL) and other specifications not included in this SAP will be described in the mock TFL.

1.1 Objectives and endpoints

Primary objective

- To evaluate the clinical efficacy of nonacog beta pegol in haemostasis (treatment of bleeding episodes during on-demand and prophylaxis [PPX]) in Chinese patients aged 12-70 years with moderate to severe haemophilia B

Secondary objectives

In Chinese patients aged 12-70 years with moderate to severe haemophilia B:

- To evaluate the clinical efficacy of nonacog beta pegol in PPX treatment (number of treated bleeding episodes during PPX)
- To evaluate the consumption of nonacog beta pegol
- To evaluate the immunogenicity of nonacog beta pegol
- To evaluate the general safety of nonacog beta pegol
- To evaluate the pharmacokinetic properties of nonacog beta pegol

1.2 Trial design

This trial is a multi-centre, open-label phase 3b trial evaluating the clinical efficacy, safety (including immunogenicity) and pharmacokinetics of nonacog beta pegol during on-demand and for prophylactic treatment in Chinese patients aged 12-70 years with haemophilia B and a FIX activity of $\leq 2\%$.

A total of 30 patients will be included in the trial (15 in each treatment arm) and a minimum 12 patients in each of the two treatment arms must complete the trial. The trial will have two arms: Arm A (on-demand/PPX treatment arm) and Arm B (PPX treatment arm including single-dose and

steady-state pharmacokinetic assessment). Patients will not be randomised to Arm A and Arm B. Whether a patient will be in Arm A or Arm B is the choice of the patient and the investigator and will be decided at the screening visit. The duration of the trial for each individual patient will be up to 64 weeks, i.e. 2 weeks screening period, up to 58 weeks treatment period (only applicable in Arm A in case a patient has no or few bleeds during the trial) and 30 days follow-up period.

Please refer to protocol section 4.1 for more details.

2 Statistical hypotheses

No confirmatory hypotheses are planned to be tested due to the low number of patients to be included in this trial.

3 Sample size determination

No formal sample size calculations have been performed. Based on meeting communication with CDE, a total number of 24 Chinese patients to complete this trial is assessed to be sufficient to evaluate efficacy and safety in the Chinese population, considering that data are also available from the global pivotal trial NN7999-3747, which included Asian patients. In order to account for withdrawn patients, 30 patients will be started on trial product (15 patients in Arm A [on-demand/PPX] and 15 patients in Arm B [PPX]).

All 15 patients in Arm B will participate in the pharmacokinetic evaluation to ensure that at least 12 patients will complete single-dose and steady-state pharmacokinetic profiles.

4 Analysis sets

All patients exposed to nonacog beta pegol in this trial will be included in the full analysis set (FAS) and the safety analysis set (SAS).

Exceptional outlier pharmacokinetic profiles and/or individual plasma FIX activities may be excluded when analysing pharmacokinetic endpoints based on the FAS. The rules to exclude data points from analysis of pharmacokinetic endpoints are described in this SAP, and the decision of data exclusion will be made during a review prior to database lock. Any excluded data points will be documented in the database lock minutes and also in the clinical trial report (CTR).

5 Statistical analyses

5.1 General considerations

Novo Nordisk will be responsible for the statistical analyses. The SAP will be finalised prior to first patient first visit.

Unless otherwise stated, all endpoints will be presented in total and by treatment regimen/period as applicable (on-demand period in Arm A; PPX period in Arm A; and Arm B [PPX]).

Summaries for continuous endpoints will include total number (N), mean (standard deviation), median and min/max and for pharmacokinetic endpoints also geometric mean and coefficient of variation (CV%). Summaries for categorical endpoints will include total number (N), number for each outcome category (n) and percentage for each outcome category (%).

FIX activities below lower limit of quantification (LLOQ) will be set to half the value of the LLOQ.

All bleeding endpoints will be evaluated based on bleeding episodes requiring treatment with haemostatic drugs. Non-treatment requiring bleeding episodes will only be listed. Bleeding episodes in relation to major surgery will also only be listed, i.e. not included in the analysis of bleeding endpoints.

Multiple bleeding locations occurring from the same event (e.g. due to a bicycle accident) or at the same time point will be counted as one bleeding episode and only one haemostatic response will be considered for the bleeding episode. In case different responses were registered for different bleeding locations in such a bleeding episode, the worst response will be used in the analysis.

A re-bleed is defined as a worsening of symptoms in the same location after an initial period of improvement, either on treatment or within 72 hours after stopping treatment. If a bleed occurs in the same location later than 72 hours after stopping the treatment it is considered a new bleed. Re-bleeds will only be considered for joint bleeds since the specific location for other bleeds e.g. in subcutaneous are not captured in the database.

In the sub-analyses of annualised bleeding rate (ABR) where there are less than 5 patients or no bleedings in a sub-group, the confidence interval will not be calculated.

5.2 Subject disposition

See mock TFLs.

5.3 Primary endpoint analysis

Endpoint title	Time frame	Unit	Details
----------------	------------	------	---------

Haemostatic effect of nonacog beta pegol when used for treatment of bleeding episodes during on-demand and PPX	From start of treatment (week 0) until end of treatment (up to week 50)	Count	Assessed as success/failure based on a four-point scale for haemostatic response (excellent, good, moderate and none) by counting excellent and good as 'success' and moderate and none as 'failure'
--	---	-------	--

This endpoint will be evaluated based on data from both Arm A and Arm B.

The primary endpoint of haemostatic effect of nonacog beta pegol will be summarised by dichotomizing into success/failure based on counting excellent and good as 'success' and moderate and poor as 'failure', and based only on reported responses. For the calculation of success rate, the numerator will include all treated bleeding episodes with a reported haemostatic response of good or excellent, while the denominator will include all treated bleeding episodes with a reported haemostatic response. Furthermore, a sensitivity analysis will be conducted, where the denominator also includes treated bleeding episodes with missing response (i.e. missing response is counted as failure).

Haemostatic effect as measured by the four-point scale will also be summarised and listed.

The haemostatic effect will be summarised in total, by cause of bleed and by location of bleed (including haemostatic effect in target joints).

Haemostatic effect for bleeding episodes in relation to major surgery will not be included in the analysis.

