#### **4.1.4 Treatment of bleeding episodes**

A treatment-requiring bleeding episode is defined as a bleed that is treated with haemostatic drugs. If a patient experiences a treatment-requiring bleeding episode it must be treated as soon as it is identified. The investigator must always be contacted in case of a severe bleed and the patient should visit the site within 24 hours, or when possible. Mild/moderate bleeding episodes can be treated at home without contacting the site. Treatment should be started as soon as a bleed is identified.

For treatment of a mild or moderate bleeding episode, for example a joint bleed, a single dose of 40 IU/kg nonacog beta pegol i.v. should be administered. If there is no observed effect of 40 IU/kg,

the investigator should be contacted prior to administration of a second dose of 40 IU/kg. A severe bleeding episode should be treated immediately at home or at a local emergency room with 80 IU/kg, and the clinical site must be contacted immediately thereafter for further instructions or transport.

During PPX treatment periods, any dose used for treatment of a bleed must be recorded as treatment of bleed and not as a PPX dose. When the bleed has resolved (e.g. pain reduction and no increase in swelling), the patient can resume the PPX dosing regimen.

If a bleeding episode occurs on a planned PPX dosing day before administration of the PPX dose, or if a bleeding episode extends into such a day, the bleeding episode must be treated with the full PPX dose (this dose should be recorded as treatment of a bleeding episode). The patient should always follow the original PPX dosing scheme unless a dose has already been given to treat a bleeding episode during the same day.

If a haemostatic response cannot be achieved after 48 hours using adequate doses of nonacog beta pegol treatment when treating bleeding episodes, another FIX product may be used at the discretion of the investigator. The use of other FIX products will result in discontinuation of trial treatment.

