### 7.1 Discontinuation of trial treatment

A patient who does not fulfil the eligibility criteria (inclusion/exclusion criteria) must not be included in the trial. Inclusion in violation of any of the eligibility criteria is non-compliant with Good Clinical Practice (GCP) procedures and must be reported to the sponsor without delay. This will be handled as an important protocol deviation, and the independent ethics committee (IEC)/institutional review board (IRB) and regulatory authorities must be notified according to local requirements. If there are no safety concerns for the patient, trial treatment may be continued or resumed at the discretion of the investigator after agreement with the sponsor's global medical expert.

A patient may be discontinued from treatment with nonacog beta pegol at the discretion of the investigator due to a safety concern.

The trial product must be discontinued, if any of the following applies for the patient:

1. Simultaneous use of an approved or non-approved investigational medicinal product in another clinical trial.
2. Haemostasis not achievable with nonacog beta pegol: The bleed cannot be controlled after 48 hours using adequate doses of nonacog beta pegol.
3. FIX inhibitors  $\geq 0.6$  and  $\leq 5$  BU, as confirmed by re-testing by central laboratory, which makes treatment (prophylaxis and/or treatment of bleeding episodes) with nonacog beta pegol clinically ineffective (see Section [8.6.2](#)).
4. FIX inhibitors  $>5$  BU as confirmed by re-testing by central laboratory.
5. Severe allergy/anaphylaxis to the trial product.
6. Use of coagulation factors FVIII, FIX and FVII-containing products other than nonacog beta pegol and other FIX-containing products such as fresh frozen plasma or cryoprecipitate (**Exception:** FIX is allowed until 120 hours before visit 2).
7. Incapacity or unwillingness to follow the trial procedures.

8. Use of anti-coagulants such as heparin and vitamin-K antagonists (heparin is allowed for sealing of central venous access devices according to local practice).
9. Use of emicizumab.
10. Anti-fibrinolitics except for local/topical use. Use of single systemic doses is allowed after careful benefit-risk evaluation.

See the flowchart in Section [1.2](#) for data to be collected at the time of treatment discontinuation (discontinuation of treatment visit; Visit 10A) and follow-up and for any further evaluations that need to be completed.

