#### **8.1.1.4 Definition of haemostatic response**

- **Excellent:** Abrupt pain relief and/or unequivocal improvement in objective signs of bleeding within approximately 8 hours after a single infusion.
- **Good:** Definite pain relief and/or improvement in signs of bleeding within approximately 8 hours after one infusion, but possibly requiring more than one infusion for complete resolution.
- **Moderate:** Probable or slight beneficial effect within approximately 8 hours after the first infusion, usually requiring more than one infusion.
- **None:** No improvement, or worsening of symptoms.

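### The primary haemostatic success rule is not linked to the protocol's own 48-hour failure event, so an uncontrolled bleed can count as a success or drop out of the rate

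*SAP*

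**What the plan says.** **Scoring.** SAP 5.3 and protocol 9.4.2 give the same rule. Successes are defined by the rating alone: "the numerator will include all treated bleeding episodes with a reported haemostatic response of good or excellent". Unrated bleeds are absent from the lower part of the fraction as well, because there "the denominator will include all treated bleeding episodes with a reported haemostatic response". A sensitivity analysis adds unrated treated bleeds to the denominator as failures. Neither section mentions rescue or discontinuation.

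**Rating.** The patient or caregiver rates the response in an open-label trial (protocol 4.1, 6.3). In protocol 8.1.1.4 the categories excellent, good and moderate are all tied to a window of about 8 hours. Good means relief or improvement "within approximately 8 hours after one infusion, but possibly requiring more than one infusion for complete resolution". None covers absence of improvement or worsening, and has no time window.

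**Failure event.** Under protocol 4.1.4, if no haemostatic response is reached after 48 hours of adequate dosing, "another FIX product may be used at the discretion of the investigator", and that use ends trial treatment. Protocol 7.1 makes the same event a mandatory reason to stop (criterion 2): "Haemostasis not achievable with nonacog beta pegol: The bleed cannot be controlled after 48 hours using adequate doses of nonacog beta pegol".

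**Which bleeds enter.** SAP 5.1 and protocol 9.4.1 admit bleeds treated with haemostatic drugs in general, so later use of another FIX product does not remove a bleed from the endpoint.

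**The concern.** The protocol names one event that is a treatment failure on its face: haemostasis could not be obtained and the product had to be stopped. The primary endpoint is haemostatic success, yet its scoring rule never refers to that event. The outcome of such a bleed therefore depends on which rating was written down, and whether one was written at all.

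If an early favourable rating stands, the clearest kind of drug failure enters the numerator. If no rating is given, it leaves the fraction altogether. Neither path can lower the success rate compared with coding the bleed as a failure. This rate is the only primary endpoint, and the data are to be compared with those of the global pivotal Trial 3747 (protocol 4.2).

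**Working it through.** There is no power or sample size figure to reproduce. SAP section 3 states "No formal sample size calculations have been performed", and the endpoint is descriptive. The check is a reading of the rules, followed by an illustration of size.

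**Step 1. How a bleed meeting criterion 2 is scored**

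| Rating reported | Primary rate | Missing-as-failure sensitivity analysis |
|---|---|---|
| Moderate or none | Failure | Failure |
| Good or excellent | Success | Success |
| No rating | Left out | Failure |

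The second row is never recoded, and the third is recoded only outside the primary result.

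**Step 2. Can the second row occur?** Take a bleed that improves within about 8 hours, then worsens and is not controlled at 48 hours. It fits good because of the early improvement, and none because of the worsening. No rule says which prevails. The worst-response rule in SAP 5.1 applies to different locations within one episode, not to successive states of one bleed. For joint bleeds, SAP 5.1 calls worsening on treatment or within 72 hours after it a re-bleed, and only later bleeding is new. It does not say what happens to the rating already given.

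**Step 3. How many bleeds could be affected?** Use of another FIX product, or meeting criterion 2, ends trial treatment, so each patient contributes at most one such bleed. That caps the number at 30. If 24 patients reach the exposure that protocol 4.1 requires for completion, the cap is 30 − 24 = 6.

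**Step 4. How many bleeds in total?** The documents give no expected count, so these are assumptions.

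- Arm A on-demand, 28 weeks, at 6 bleeds a year (the 12-month minimum for on-demand patients in inclusion criterion 5): 15 × 6 × 28/52 = 48.5.
- Arm B, 50 weeks, at the rate of 1.90 in protocol 2.2: 15 × 1.90 × 50/52 = 27.4.
- Arm A prophylaxis, 16 to 30 weeks at 1.90: 15 × 1.90 × 16/52 = 8.8, to 15 × 1.90 × 30/52 = 16.4.
- Total: 84.6 to 92.3, or about 85 to 92.
- Higher case, with an assumed on-demand rate of 15 that is not in the documents: 15 × 15 × 28/52 = 121.2, and 121.2 + 27.4 = 148.6, about 150. This leaves out Arm A's prophylaxis bleeds; adding them gives 157 to 165.

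**Step 5. Size.** With N bleeds and k moved from success to failure, the rate falls by k/N. For k = 1 this is 1/85 = 1.2 points to 1/150 = 0.7 points (0.6 at 157 to 165). If the k bleeds were left out instead, and s of the others are successes, the fall is s/(N − k) − s/N. Taking success in the other bleeds at 93.2% (protocol 4.3, rounded to whole bleeds):

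| N | k | Left out | As success | As failure | Success minus failure | Left out minus failure |
|---|---|---|---|---|---|---|
| 90 | 1 | 93.3% | 93.3% | 92.2% | 1.1 | 1.0 |
| 90 | 3 | 93.1% | 93.3% | 90.0% | 3.3 | 3.1 |
| 90 | 6 | 92.9% | 93.3% | 86.7% | 6.7 | 6.2 |
| 150 | 1 | 93.3% | 93.3% | 92.7% | 0.7 | 0.6 |
| 150 | 3 | 93.2% | 93.3% | 91.3% | 2.0 | 1.9 |
| 150 | 6 | 93.1% | 93.3% | 89.3% | 4.0 | 3.7 |

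Results are also shown by regimen. In Arm B alone, with about 27 bleeds, one bleed is 1/27 = 3.7 points.

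**The case against.** The case for leaving the plan alone is substantial.

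- Protocol 4.1.4 allows another FIX product only when no haemostatic response could be achieved, which is what the scale measures. The category none has no 8-hour limit and includes worsening, so most of these bleeds should already be rated as failures. This stands, and it is the main reason to expect a small effect.
- Protocol 8.7 requires the rating to be checked with the patient at visits, and 8.1.1 makes the investigator responsible for correct diary data. A favourable rating on an uncontrolled bleed should be queried. This stands as review. It is not an override: only the patient or caregiver may change a response, and no criterion says that an uncontrolled bleed cannot be rated good.
- For a hospitalised patient the investigator reports the bleed in the eCRF (8.1.1), and any rating still missing counts as failure in the planned sensitivity analysis. This largely answers the missing-rating route, though not in the primary rate.
- The SAP says "No confirmatory hypotheses are planned to be tested due to the low number of patients to be included in this trial", and there is no success threshold. This limits the consequence, not the direction of the error.

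A reader might infer that the plan scores rescued bleeds as successes. It does not say so: it leaves two categories overlapping without a precedence rule. A reader might also infer that any use of another FIX product should be a failure. Protocol 7.1 lists such use (criterion 6) separately from uncontrolled haemostasis (criterion 2), so use for other reasons is not evidence that the drug failed.

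**Conclusion.** The gap is real but narrow. No section of either document sets a bleed that meets the protocol's 48-hour failure criterion to failure. An early good rating can survive in every planned analysis. A missing rating removes the bleed from the primary rate, with recovery only in the sensitivity analysis.

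Compared with coding as failure, the bias runs one way, towards a higher success rate. Its size is uncertain and probably small: about 0.7 to 1.2 percentage points per bleed moved from success to failure, if there are 85 to 150 bleeds in total. The bleed counts, and the one, three or six affected bleeds in the tables, are illustrations; the documents forecast neither. The documents do not support a claim that the planned rate will be materially inflated. They do support settling the rule before database lock, because otherwise the few clearest failures would be scored case by case.

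**What to change.** Add to SAP 5.3 and protocol 9.4.2: a bleeding episode that meets criterion 2 of protocol 7.1, or for which another FIX product was given to treat that same bleed because haemostasis was not achieved with nonacog beta pegol, counts as failure whatever its four-point rating, including a missing rating. State that use of another FIX product for any other reason does not trigger the rule.

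List these bleeds individually with their ratings. Keep the planned reported-responses-only rate as a sensitivity analysis, so that a rate under that rule remains available for the comparison with Trial 3747, whose own scoring rule the documents do not give. In the same edit, correct the SAP 5.3 text that calls the lowest category poor; the scale calls it none.

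The cost is a few sentences and one listing. The success rate may be slightly less favourable. The rescue record must also be matched to the individual bleed: protocol 6.5 records other medication with indication and dates, and 7.1 records one primary reason for discontinuation, but neither is stated to be linked to a particular bleed. Matching by date and indication should be specified. No dose, rescue or stopping rule changes.

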5.4 Secondary endpoints analysis

5.4.1 Secondary efficacy endpoints

Endpoint title	Time frame	Unit
Number of treated bleeding episodes during PPX treatment (Arm B only)	From start of treatment (week 0) until end of treatment (week 50)	Count
Consumption of nonacog beta pegol for treatment of bleeding episodes	From start of treatment (week 0) until end of treatment (up to week 50)	IU/kg per bleed

Consumption of nonacog beta pegol for PPX treatment (Arm B only)	From start of treatment (week 0) until end of treatment (week 50)	IU/kg per year
FIX trough levels during PPX treatment (Arm B only)	From start of treatment (week 0) until end of treatment (week 50)	IU/mL

5.4.1.1 Number of treated bleeding episodes during PPX treatment

This endpoint will be evaluated based on data from Arm B only.

This endpoint will be analysed by a Poisson regression model allowing for over-dispersion (using Pearson's chi-square divided by the degrees of freedom) with the logarithm of prophylaxis duration used as offset. Estimates of ABR will be provided with 95% confidence intervals.

Only the observed bleeding episodes will be counted and the offset will be actual PPX duration.

A sensitivity analysis based on negative binomial regression model with the logarithm of PPX duration used as offset will also be performed.

Another sensitivity analysis will be performed imputing the number of bleeding episodes for withdrawals. Specifically this will be done by using a last observation carried forward (LOCF) approach for all patients with at least 1 month PPX treatment duration by calculating the yearly bleeding episode rate for withdrawn patients and use that as endpoint. As an example a patient with 6 bleeding episodes in 4 months will have an endpoint value of 18 corresponding to a maintained bleeding rate of 18 bleeding episodes per year. For patients withdrawing within 1 month, this method is considered to give too uncertain LOCF values, hence imputation will not be attempted for such patients.

ABRs will be summarised in total, by cause of bleed, and by location of bleed (including ABR in target joints).

Bleeding episodes in relation to major surgery will not be included in the analysis.

ABR will also be performed separately for patients coming from an on-demand regimen and a PPX regimen. For both groups the ABR will be compared descriptively to the ABR immediately prior to initiation of PPX with nonacog beta pegol.

